Given the current lack of evidence on particle aerosolization during endoscopy, we plan to conduct a randomized controlled trial utilizing a commercially available particle detector to assess particle suspension in the air during upper endoscopic procedures. We hypothesize that use of an endoscopic patient facemask reduces periprocedural aerosolization during upper endoscopic procedures. Our initial effort will be focused on conducting a pilot trial to assess population variability as no baseline data exists for aerosolization in the general population. We hope to subsequently conduct a larger scale trial to fully test our hypothesis. If an endoscopic facemask significantly reduces aerosolization it could be used to decrease infectious risk to providers while posing minimal risk to the patient and without significantly altering the endoscopic procedure.

Methods

Study Design: Prospective randomized controlled trial

Sample Population

- All patients presenting for an elective upper endoscopic procedure with monitored anesthesia care
- For the pilot trial we plan to recruit 50 total patients, 25 patients in the control arm without a procedural facemask and receiving 2-4 L/min of oxygen via nasal cannula and 25 with a specially designed facemask. An additional 10 patients will be enrolled to account for subject dropout as necessary. Sample size calculation was conducted for the purpose of estimating population variability with a 0.05 level of significance and 0.8 power level. This was done with the assistance of the Department of Quantitative Health Sciences at the Cleveland Clinic
- Inclusion Criteria:
 - All patients undergoing elective upper endoscopic procedures (upper endoscopy, ERCP, endoscopic ultrasound) with monitored anesthesia care at main campus Cleveland Clinic Q3 inpatient endoscopy unit.
- Exclusion Criteria:
 - Any patient requiring endotracheal intubation
 - Pregnant patients
 - Emergency procedures
 - Patients who require use of a facemask before or during the procedure due to medical necessity
 - Patients under the age of 18
 - Non-English speaking individuals
 - Patients unable to provide consent.
 - Any procedure done outside the designated procedure room.
 - If in the opinion of the anesthesiologist, a subject who was randomized to the control arm requires placement of the procedural mask to augment oxygenation, the subject will be removed from the study

Research Procedure:

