- All patients undergoing an upper endoscopic procedure in the designated procedure room with monitored anesthesia care will be eligible for recruitment into the study once exclusion criteria are applied
- Patients will be randomized to receive an endoscopic procedural facemask or to undergo endoscopy without one at the time of enrollment in the pre-procedure holding area. Control subjects will receive supplemental oxygen (2-4 L/min) via nasal cannula as per our standard protocol. Use of this mask will not affect the risk of the procedure nor change the nature of the patient's endoscopy in any way. An example of this commercially available facemask is pictured below. The mask is currently used in the inpatient endoscopy unit at the main campus of the Cleveland Clinic is selected patients for oxygen delivery.

- In order to collect particle aerosolization data, use of a Met One GT-526S Handheld Particle Counter will be used. This device can detect particles of six different sizes ($0.3\mu\text{m}$, $0.5\mu\text{m}$, $1\mu\text{m}$, $2\mu\text{m}$, $5\mu\text{m}$ and $10\mu\text{m}$). This data can be directly downloaded from the device using the associated Comet software. Device pictured below:

- Endoscopy will be performed in accordance with standard procedures at the Main Campus Cleveland Clinic by either a staff gastroenterologist or a gastroenterology fellow trainee under direct supervision by a staff gastroenterologist.

- The device will be placed in a standardized position 12 inches from the head of the subject on a tripod. The device location will not hinder access to the subject by anesthesia, nursing or gastroenterology staff.

Data Collection:

- Data collected before the patient enters the procedure room:
 - Patient Demographics (age, gender)
 - BMI
 - Upper Endoscopic Procedure Type (ex: esophagogastroduodenoscopy, endoscopic ultrasound, endoscopic retrograde cholangiopancreatography)
 - Patient Mallampati Score
- Data collected in the procedure room prior to start of endoscopy:
 - Patient vitals including BMI and oxygen saturation
 - Patient positioning (left lateral decubitus, supine, prone).
 - Oxygen flow rate being administered by anesthesia staff
 - Number of individuals in the room
 - Peak and mean aerosolized particle counts for 5 minutes prior to endoscopy start
- Data collected during the procedure
 - Any change in supplemental oxygen requirement

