 - Any intra-procedural manipulation of the patient's head and neck (ie. head tilt, jaw thrust)
 - Any removal and reinsertion of the endoscope
 - Any opening of the designated procedure room door
 - Any use of the endoscope working channel
 - Peak and mean aerosolized particle counts. This will be obtained during three intervals for six different sizes (0.3 μ m, 0.5 μ m, 1 μ m, 2 μ m, 5 μ m and 10 μ m). The three intervals are: A. A 5-minute baseline period before initiation of sedation. B. Intra-procedurally and C. Post procedurally for 5 minutes, which is defined as beginning after the endoscope is removed.
- Data collected post-procedurally
 - Total procedure duration
 - Total dosage of medications utilized for sedation
 - Use of any reversal agents
 - Peak and mean aerosolized particle counts for 5 minutes after endoscopy completed
- After the patient exits the procedure room no further patient data will be collected
- Post-procedurally patients will follow standard post endoscopy monitoring prior to discharge.

Sample Size Calculation and Data Analysis

Sample size calculation was conducted for the purpose of estimating population variability with a 0.05 level of significance and 0.8 power level. This was done with the assistance of the Department of Quantitative Health Sciences at the Cleveland Clinic.

Data will be described using means (standard deviations) for normally distributed continuous variables, medians [quartiles] for non-normally distributed continuous variables, and frequency (percentage) for categorical variables. Shapiro-Wilks test will be conducted for continuous variables to assess normality. Analysis of variance (ANOVA) or the non-parametric Kruskal-Wallis tests will be used to assess differences in continuous variables. The chi-square test and Fisher's exact test will be used to compare categorical variables as appropriate. A linear mixed model will be used to assess the association between the clinical factors and concentration level of each particle. The mixed model will be used to account for

within subject correlation. All tests will be two-tailed and performed at a significance level of 0.05.

Analyses will be performed using R software

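### The plan does not say which analysis gives the mask effect, and a model that put arm beside factors recorded after randomisation could estimate something other than the randomised effect.

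*Combined protocol and SAP*

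**What the plan says.** Three parts of the protocol bear on this point.

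- **Analysis methods** (Sample Size Calculation and Data Analysis). For group differences: "Analysis of variance (ANOVA) or the non-parametric Kruskal-Wallis tests will be used to assess differences in continuous variables". The groups and intervals to be compared are not named. The only regression follows: "A linear mixed model will be used to assess the association between the clinical factors and concentration level of each particle". Its stated purpose is to handle correlation within a patient ("The mixed model will be used to account for" this). The factors are not listed, and arm, interval and their interaction are not mentioned.
- **Hypothesis and endpoint** (same section). The endpoint is the concentration of each of six particle sizes over three intervals. The hypothesis is that the mask lowers all sizes during the procedure relative to controls. No sentence links it to a particular analysis.
- **Timing** (Research Procedure and Data Collection). Patients are randomised "at the time of enrollment in the pre-procedure holding area". One group of variables falls under "Data collected before the patient enters the procedure room". The others are recorded in the room before endoscopy, during the procedure or afterwards. They include "Any change in supplemental oxygen requirement" and "Total dosage of medications utilized for sedation".

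**The concern.** The randomised comparison is protected only while the model conditions on things that the mask cannot have changed. The mixed model is the only method said to deal with repeated measurements on a patient, so an analyst could well add arm to it and report that coefficient as the mask effect. If the model also holds factors that arise after randomisation and respond to the mask, the coefficient no longer estimates the total effect of assignment.

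The protocol itself gives reason to think that some factors could respond. Controls receive 2-4 L/min by nasal cannula, and the mask is described as a device already used to deliver oxygen. The exclusion criteria foresee a control who "requires placement of the procedural mask to augment oxygenation". Oxygen flow and changes in oxygen requirement are therefore tied to arm, and airway manoeuvres such as jaw thrust plausibly are too.

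Two things are at stake: which of several estimates is reported as the mask effect, a choice now left open until the data are in hand, and whether that estimate is the randomised one.

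**Working it through.** **The plan's own figure.** The plan gives no figure for this point. Its only design figure is 50 patients (25 per arm) at a 0.05 level and 0.8 power. That figure cannot be reproduced because no effect size or SD is stated. For scale only, 25 per arm detects √(2/25) × (1.960 + 0.842) = 0.79 SD, two-sided, with 80% power.

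**Step 1: count the candidate factors.** The source is the Data Collection lists, with particle counts left out and BMI counted once.

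- Before room entry: age, gender, BMI, procedure type, Mallampati score = 5.
- In the room before endoscopy: vitals with oxygen saturation, positioning, oxygen flow, number of people = 4.
- During the procedure: oxygen change, head or neck manipulation, scope reinsertion, door opening, working-channel use = 5.
- Afterwards: duration, sedation dose, reversal agents = 3.

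The total is 5 + 4 + 5 + 3 = 17. Recorded after randomisation: 4 + 5 + 3 = 12 of 17 (71%). Recorded during the procedure: 5 of 17 (29%), or 8 of 17 (47%) with duration, sedation dose and reversal agents.

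**Step 2: what adjustment does to the arm coefficient.** Take one yes/no factor with frequency p0 in controls and p1 in the mask arm, effect b on the outcome, and direct mask effect d. With no unmeasured cause shared by factor and outcome:

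- total effect = d + b(p1 − p0)
- adjusted coefficient = d
- gap (adjusted minus total) = −b(p1 − p0)

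A shared cause adds a further gap whenever p1 differs from p0, even if b = 0. That part was obtained by simulating 1,000,000 patients.

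The documents supply none of these inputs, so all are assumed: d = −0.8, error SD 1, p0 = 40%, p1 − p0 of 0 or ±20 points, b from 0 to 1.0, and a shared cause that is absent or has loading 0.7.

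| p1 − p0 | b | Shared cause | Total | Adjusted | Gap |
|---|---|---|---|---|---|
| 0 | 0, 0.5 or 1.0 | no or yes | −0.80 | −0.80 | 0.00 |
| −0.2 | 0 | no | −0.80 | −0.80 | 0.00 |
| −0.2 | 0.5 | no | −0.90 | −0.80 | +0.10 |
| −0.2 | 1.0 | no | −1.00 | −0.80 | +0.20 |
| −0.2 | 0 | yes | −0.80 | −0.67 | +0.13 |
| −0.2 | 1.0 | yes | −1.00 | −0.67 | +0.33 |
| +0.2 | 0.5 | no | −0.70 | −0.80 | −0.10 |
| +0.2 | 1.0 | no | −0.60 | −0.80 | −0.20 |
| +0.2 | 1.0 | yes | −0.60 | −0.93 | −0.33 |

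If the mask makes the factor rarer, adjustment shrinks the apparent benefit. If it makes the factor more common, adjustment enlarges it. If it leaves the factor alone, nothing changes.

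**The case against.** The strongest reply is that the plan never puts arm in the mixed model. Read plainly, the sentence describes an association analysis, and the ANOVA or Kruskal-Wallis tests can supply an unadjusted randomised comparison. This stands, and it is why the distortion is only a possibility. It does not close the gap: the tests are not tied to the hypothesis, and an unadjusted comparison makes no use of the baseline count.

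Being recorded after randomisation is also not the same as being changed by the mask. Door openings and the number of people in the room have no obvious link to arm, and the Research Procedure section asserts that the mask leaves the endoscopy unaltered. That assertion counts for something, but it is not evidence that oxygen needs or airway manoeuvres are equal between arms.

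Controls who need the mask are removed from the study, so they would not enter the model. The exclusion criterion shows only that the protocol expects the mask to influence oxygenation.

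Finally, this is a pilot meant to assess variability, with a larger trial to follow. That lowers the stakes, but the plan still states a mask hypothesis and two-sided tests at 0.05.

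A reader might infer that most of the factors are in-procedure events. The lists do not support this: the count is 5 of 17, or 8 at the widest. Nor do the documents show that the factors enter together, since one-factor-at-a-time models fit the sentence equally well.

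**Conclusion.** The point holds as a gap in the plan with a possible consequence. The plan does not name the analysis that gives the mask effect or the terms of its only regression, and 12 of the 17 candidate factors are recorded after randomisation. A coefficient for arm could be distorted if three conditions hold together: arm is entered, a factor in the model is shifted by the mask, and that factor affects the counts or shares a cause with them. Under the assumed inputs the gap runs from 0.00 to about 0.33 error SDs, in either direction.

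A reader might go further and conclude that the mask estimate will be biased, or that it will be pulled towards no effect. The documents support neither conclusion, because they do not say that arm is in the model and give no data on whether or which way the mask shifts any factor. The change is still worth making, because it replaces an open choice with a defined and better estimate from data already being collected.

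**What to change.** Amend the data analysis section before the data are examined.

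1. **Mask effect.** For each particle size, fit a linear mixed model with arm, interval (during and after the procedure), arm-by-interval and a random patient effect. Name the arm contrast during the procedure as the answer to the hypothesis. Enter the 5-minute baseline count as a covariate, and do not also use it as an outcome row. Otherwise adjust only for factors fixed before randomisation, such as procedure type, BMI, age, gender and Mallampati score. Being known before endoscopy is not a sufficient criterion, because oxygen flow, saturation and positioning are recorded in the room after allocation.
2. **Baseline interval.** State whether the mask is on while the baseline count is taken, which the documents do not say. If it is, the baseline may already carry some mask effect, so report the estimate without baseline adjustment as well.
3. **Other factors.** Put in-procedure and other post-randomisation factors in a separate model labelled exploratory, and draw no mask-effect claim from it.

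The cost is SAP wording and slightly more analysis work. No new data are needed.

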Research Protocol

Title: Does Use of a Facemask Reduce the Risk of Aerosolization During Anesthesia Assisted Upper Endoscopic Procedures: A Randomized Controlled Pilot Trial

PI: [name] [name]

Co-Investigators: [name] MD, [name], MS, [name], MD, MS, [name], MS, [name], [name], [name], [name], [name], [name], [name].

Introduction

There is little evidence describing the aerosolization of potentially infectious particles during gastrointestinal endoscopy. Such a phenomenon could potentially place medical staff and patients alike at exposure risk despite the use of personal protective equipment as once aerosolized, microscopic water droplets could remain suspended in the air for hours and represent a potential risk of spread of infectious agents. We propose a randomized controlled pilot trial to assess aerosolization and the potential use of an endoscopic patient facemask to reduce the risk of viral transmission.

Background and Significance

Unfortunately there is a lack of data regarding infectious risk posed to healthcare providers by aerosolization during upper endoscopy. Furthermore, the current COVID-19 pandemic has heightened stress surrounding the danger of potential aerosolizing procedures. While personal protective equipment may reduce some risk, aerosolized particles can remain suspended in the procedural room environment and may lead to transmission despite the use of personal protective equipment. There is only one prospective observational study assessing aerosolization during endoscopy, which used a handheld particle detector in 93 patients undergoing upper endoscopy and found significant increases in particle suspension within the air in the endoscopy procedure room at a distance from the subject where the endoscopist and support staff would be located.

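### Patients share one room's air, but the models allow only for within-patient correlation: the mask test stays valid, while tests of clinical factors that cluster by day could be too liberal

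*Combined protocol and SAP*

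**What the plan says.** The Exclusion Criteria rule out "Any procedure done outside the designated procedure room", and Research Procedure repeats the restriction to that room. The Introduction gives the reason for concern about room air: "once aerosolized, microscopic water droplets could remain suspended in the air for hours". Patients are randomised one by one in the holding area.

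Under Sample Size Calculation and Data Analysis, a linear mixed model relates clinical factors to the concentration of each particle size. The stated purpose of the mixed structure is to handle "within subject correlation. All tests will be two-tailed and performed at a significance level of 0.05". ANOVA or Kruskal-Wallis is planned for other continuous comparisons, and both treat patients as independent.

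The Data Collection lists cover door openings, the number of people in the room and a 5-minute baseline count before sedation. Apart from total procedure duration they hold no time item: no date, clock time, case order or time since the previous case. The primary endpoint is the concentration in each of the three intervals. The plan does not say that baseline enters as a covariate or is subtracted.

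**The concern.** If particles can persist, two patients treated in the same room on the same day share an ambient level. The later one may also inherit residue from the case before, masked or not, in the study or not. Their readings are then correlated. A patient-level intercept does not capture this, because it treats different patients as independent.

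At stake are the standard errors for between-patient factors that tend to run together on a list day. Procedure type, patient position and the number of people in the room are plausible examples. The precision of the mask contrast is also affected, since room-day variation stays in its error term.

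**Working it through.** **The plan's own figure.** The plan states: "For the pilot trial we plan to recruit 50 total patients, 25 patients in the control arm without a procedural facemask", with 0.05 significance and 0.8 power but no effect size or SD. The figure therefore cannot be derived from the plan. It is compatible with a standardised difference d of 0.8: n per arm = 2(1.96 + 0.842)²/0.8² = 15.70/0.64 = 24.5, so 25. That calculation treats patients as independent. I use d = 0.8 below only as a reference point.

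**Inputs.** From the documents: 50 patients, individual randomisation, one room, two-sided 0.05. Assumed, because the documents are silent: m = 2 to 4 study patients per day, and same-day correlation ρ = 0.2 to 0.4 for a reading in a single interval.

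**Factor shared by everyone on a day.** The true variance of the comparison exceeds the variance computed without a day term by about DE = 1 + (m − 1)ρ. The actual type I error is then about 2[1 − Φ(1.96/√DE)].

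| m | ρ | DE | 1.96/√DE | Type I error |
|---|---|---|---|---|
| 1 | any | 1.0 | 1.960 | 5.0% |
| 2 | 0.2 | 1.2 | 1.789 | 7.4% |
| 2 | 0.4 | 1.4 | 1.657 | 9.8% |
| 3 | 0.2 | 1.4 | 1.657 | 9.8% |
| 3 | 0.4 | 1.8 | 1.461 | 14.4% |
| 4 | 0.2 | 1.6 | 1.550 | 12.1% |
| 4 | 0.4 | 2.2 | 1.321 | 18.6% |

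Simulating 50 patients with a t-test that ignores day agrees to within about half a percentage point. Across separate simulations the lowest setting came out at 7–8% and the highest at about 19%. With a random day intercept the error returned to about 4–5%.

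**Mask contrast.** Arm is assigned within days at random, so a shared day level falls on both arms alike. Simulated type I error with day ignored was 0.048 to 0.051 for ρ from 0 to 0.5, with 2 or 5 patients per day. Carry-over of 0.2 or 0.5 of the previous reading left it at 0.050 to 0.051.

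Precision is what changes. At d = 0.8, with 2 to 4 per day and a day share of 0.2 to 0.4, adding a random day intercept moved power from about 0.80 to between 0.80 and 0.91. There was no loss when the day effect was zero. Under a heavier assumption (5 per day, ρ = 0.3), carry-over of 0.2 or 0.5 cut power from 0.80 to 0.74 or 0.57. With day in the model it was 0.83 or 0.71.

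**Random rather than fixed day effects.** With 2 per day and ρ = 0.3 or 0.5, fixed day effects lowered power to 0.63 or 0.76, against 0.79 or 0.80 with day ignored.

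**The case against.** The strongest reply is that the trial's hypothesis concerns mask against control, which is individually randomised, so nothing is wrong with its main test. That stands. A reader might infer from the shared room that the mask comparison is invalid or its p-values too small. The design does not support that reading, and the simulations contradict it.

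Other replies also carry weight:

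- **Baseline.** Each patient's 5-minute baseline already measures that day's background plus any residue. A room level constant over the three intervals is absorbed by the patient intercept for within-patient contrasts. So it would be wrong to say that the shared air cannot be adjusted for at all. What remains is that the plan does not specify using the baseline, and the patient intercept does not protect between-patient factors.
- **Day-constant factors.** The table is a worst case. BMI, Mallampati score, head manipulation and sedation dose vary by patient, and no document shows that any factor clusters by day.
- **Persistence.** The Introduction says particles could stay suspended, not that they do. Air exchange, gaps between cases and cases per day are not given.
- **Field list.** It also omits the randomised arm, so it is not exhaustive. A missing date shows that date is not planned for analysis, not that it is unobtainable.
- **Understated rise.** One might infer that residue shrinks the apparent rise during endoscopy. That holds clearly for a percentage rise, but the plan's endpoint is concentration. A constant residue leaves the absolute rise unchanged.
- **Pilot status.** Full testing is deferred to a larger trial, which limits the harm from a liberal association test. But the pilot exists to measure variability. With same-day correlation the SE of the estimated variance grows by about √(1 + (m − 1)ρ²): √1.04 = 1.02 at m = 2, ρ = 0.2, and √1.48 = 1.22 at m = 4, ρ = 0.4.

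**Conclusion.** The omission is real, and its consequence is limited. The planned mask test holds its 5% level and may forgo some precision. The non-randomised clinical-factor models are exposed: a factor fully shared within a day would be tested at roughly 7–8% to 19% instead of 5%. That range rests on an assumed 2 to 4 study patients per day and a same-day correlation of 0.2 to 0.4. Partial sharing gives less inflation, and one patient per day gives none. Since the plan supplies neither quantity, the range illustrates what could happen and does not estimate what will. This is a cheap improvement worth making before enrolment, not a flaw that undermines the trial.

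**What to change.** 1. Record the procedure date, the clock times of the three intervals, and the end time and mask status of the previous case in the room, whether or not it was a study case.
2. Add a random intercept for procedure date to the mixed models, including the model used for the mask contrast.
3. Adjust the procedural and post-procedural comparisons for each patient's own 5-minute baseline, which is already collected. State whether the mask is in place during that baseline, because adjusting for a baseline already affected by the mask would remove part of its effect.
4. Use time since the previous case only in a sensitivity analysis. It is undefined for the first case of the day, so code those cases as a separate category.

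The cost is a few database fields and one more variance component. If few patients share a day, that component will be imprecisely estimated. With one patient per day it cannot be separated from the patient effect; the report should then say so, and the day term can be dropped.
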